#### 7.7.1. Pulmonary Function

Pulmonary function testing will be completed to evaluate the maximal lung function recording FVC, FEV1, MIP and MEP.

#### 7.7.2. 4 Stair Climb (4 SC)

The 4 SC quantifies in seconds the time required for a subject to ascend 4 standard steps. The method the subject uses (eg, using the hand rails) to climb the stairs is recorded to understand any change in technique that occurs over time.

#### 7.7.3. 10-meter walk/run

The 10-meter walk/run is a frequently used timed function test in muscular dystrophy trials demonstrating good test-retest reliability in several different populations and has been used in studies of LGMD2I. Individuals are instructed to walk at a fast but comfortable speed in a long cooridor with an even surface. Measurement of time begins at a still-standing start and stops when the individual passes the 10-meter mark while continuing to walk 2.5 meters beyond the mark.

#### 7.7.4. Timed Up & Go (TUG)

The Timed Up & Go is a measure of hip strength as well as dynamic balance. This timed function test has good test-retest reliability and has been used in studies of LGMD2I. The individual is asked to rise from a seated position in a standardized armchair (44-45 cm), walk at a comfortable and safe pace to a tape mark on the floor 3 meters away, turn around the mark, go back to the chair, turn and sit down.

#### 7.7.5. Strength Assessment

Muscle strength will be quantified by means of manual muscle testing (MMT) quantified by the modified Medical Research Council (MRC) scale and by handheld dynamometer

quantified in pounds (lbs). The following muscle groups will be evaluated: shoulder abduction, elbow flexion, elbow extension, hip extension, hip flexion, knee extension, knee flexion.

# 7.7.6. Performance of Upper Limb (PUL)

The PUL scale has been devised to assess motor performance of the upper limb. Motor performance will be impacted by muscle strength and contactures and the scale aims to incorporate performance of shoulder, elbow, wrist and hand function.

# 7.7.7. Two Minute Walk Test (2MWT)

The 2-minute walk test (2MWT) is a shorter measure of walking performance than the 6minute walk test (6MWT). In this test, subjects start from a clearly marked line of tape on the floor and walk up and down a 21 meter hallway for 2 minutes at a fast but comfortable speed wearing their regular footware. The 6MWT has been used extensively in pediatric DMD trials . The 2MWT may be more feasible in populations such as LGMD2I where the 6MWT is too fatiguing. Studies of the 2MWT in adult patient populations have reported good testretest and interrater reliability .

# 7.8. Quality of Life Assessments

# 7.8.1. InQoL

This survey consists of 45 questions within 10 sections. Four sections focus on the impact of key muscle disease symptoms (weakness, locking, pain, and fatigue), five look at the impact (degree and importance of impact) muscle disease has on particular areas of life, and one section asks about the positive and negative effects of treatment .

#### 7.8.2. SF-36

This questionnaire is a multi-purpose, short form patient-reported health survey with only 36 questions. It is a generic measure, providing an 8-scale profile of functional health as well as measuring physical and mental health. Each scale is transformed into a 0-100 scale, with a score of 0 being equivalent to maximum disability and a score of 100 being indicative of no disability . It provides a measure of relative disease burden and allows differentiating the health benefits produced by various different treatments.

#### 7.9. Needle Muscle Biopsy

Needle muscle biopsy is used to obtain small amounts of tissue (milligrams) for molecular studies in a clinic setting without the requiment of recovery time. Needle muscle biopsies have been used previously in clinical trials of muscular dystrophy for this purpose where histology is not needed . In this procedure, the skin overlying the tibialis muscle is sterilely prepped and local anesthesia (1% lidocaine with 1:100,000 epinephrine) is infused subcutaneously and into the soft tissue to be biopsied. A nick is made in the skin with the tip of a scalpel. Through the skin incision, measuring less than 0.5 cm, a 14 gauge biopsy needle is inserted. Several small samples of skeletal muscle can be withdrawn through the same skin incision with the biopsy needle, each measuring less than 0.5 cm by 0.02 cm. A sterile bandage is applied following the procedure.

#### 7.10. Triggered Requirements

Condition/ Criteria	Action
Moderate Iron overload/ If the liver iron content	The subject should be referred to a hepatologist for
estimate as determined by R2* value is above the "mild	further assessment
overload" range (R2* >369 Hz at 3.0 T	
Cardiomyopathy/ If the LVEF falls 10% of baseline on	The subject should be referred to a cardiologist for
the cardiac echocardiogram at any follow-up visit	further assessment.

#### 7.11. Infusion Site Monitoring

From the initiation of the IV infusion subjects will be monitored for signs of any infusion site reactions including but not limited to erythema, swelling, bruising, pain or prutitis.

#### 8. ADVERSE EVENT REPORTING

#### 8.1. Adverse Events

All observed or volunteered AEs regardless of treatment group or suspected causal relationship to the investigational product(s) will be reported as described in the following sections.

For all AEs, the investigator must pursue and obtain information adequate both to determine the outcome of the AE and to assess whether it meets the criteria for classification as an serious adverse event (SAE) requiring immediate notification to Pfizer. For all AEs, sufficient information should be obtained by the investigator to determine the causality of the AE. The investigator is required to assess causality. Follow-up by the investigator may be required until the event or its sequelae resolve or stabilize at a level acceptable to the investigator, and Pfizer concurs with that assessment.

As part of ongoing safety reviews conducted by the sponsor, any nonserious AE that is determined by the sponsor to be serious will be reported by the sponsor as an SAE. To assist in the determination of case seriousness, further information may be requested from the investigator to provide clarity and understanding of the event in the context of the clinical study.

#### 8.2. Reporting Period

For SAEs, the active reporting period to Pfizer begins from the time that the subject provides informed consent, which is obtained prior to the subject's participation in the study, ie, prior to undergoing any study-related procedure and/or receiving investigational product, through and including 112 calendar days after the last administration of the investigational product. SAEs occurring to a subject after the active reporting period has ended should be reported to Pfizer if the investigator becomes aware of them; at a minimum, all SAEs that the investigator believes have at least a reasonable possibility of being related to study drug are to be reported to Pfizer.

• AEs (serious and nonserious) should be recorded on the Case Report Form (CRF) from the time the subject has taken at least 1 dose of study treatment through the last subject visit.

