## Cohort 3 (n=8):

- Lead-in period (16 weeks)
- Treatment: PF-06252616 40 mg/kg (32 weeks)
- Follow-up period (16 weeks)
- Extension period: PF-06252616 40 mg/kg (24 weeks)

[figure not shown]
At each dose level, subjects will be followed for an initial approximate 16-week lead-in period to establish individual change in disease progression.

The study will begin with 4 subjects being enrolled into Cohort 1. Following the lead-in period, subjects in Cohort 1 will be dosed with 5 mg/kg for a total of 32 weeks (8 doses). Cohort 2 will begin dosing at the mid dose level (20 mg/kg) once safety has been confirmed with subjects in Cohort 1 who have been treated for 16 weeks. Cohort 1 and 3 will begin dosing at the highest dose level (40 mg/kg) once safety has been confirmed with subjects in Cohort 2 who have been treated for 16 weeks.

Each dose level will be evaluated for 32 weeks (8 doses each). Cohort 1 is the only cohort who will receive 2 dose levels (5 mg/kg and 40 mg/kg) and their total treatment time will be a minimum of 64 weeks. Subjects in Cohort 1 will only receive 8 doses of the 5 mg/kg dose and not proceed to the 40 mg/kg dose until safety review and approval by the SMC.

At the conclusion of the treatment period, subjects will be followed for an additional 16 weeks to monitor for safety, PK and duration of response.

All subjects completing the follow-up period will have the option to continue treatment with 40mg/kg dose in the Extension Period.

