## 3.2. Duration of Subject Participation

Subject's participation will begin during screening (up to 2 weeks) followed by a lead-in period (16 weeks), treatment period (64 weeks for Cohort 1, 32 weeks for Cohorts 2 and 3), follow-up period (ending 16 weeks after the last study dose in the treatment period), and the extension period (up to 28 weeks for Cohort 1, up to 40 weeks for Cohort 2, and up to 24

weeks in Cohort 3). Periods of participation are estimates and are dependent on enrollment and safety review of concurrent dosing cohorts. Subjects will return to the site monthly for study drug administration as well as completion of safety and efficacy assessments.

In order to ensure consistency in assessment collection, visits that include functional assessments and imaging assessments (DXA and WB-MRI) will be collected over 2 consecutive days, within the study visit window. In the case where subjects are traveling from a distance, the site will offer nearby overnight accommodations.

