# 6.4. Active Treatment: Visit 4 (Day 29±3), 8 (Day 141±3), 10 (Day 197±3) and for Cohort 1, Visit 12 (Day 253±3), 16 (Day 365±3), 18 (Day 421±3)

- **Pregnancy Test**: A highly sensitive urine pregnancy test will be performed on all female subjects
- Diary Cards: For collection of first day of each menstrual cycle for WOCBP.
- Contraception Review: Confirmation of use of acceptable forms of contraception
- Weight
- Vital Signs: Supine blood pressure, pulse rate, respiratory rate, and oral temperature.
- Clinical laboratory testing:
  - Hematology with complete blood count and differential, comprehensive metabolic panel (sodium, potassium, chloride, carbon dioxide, blood urea nitrogen, creatinine, calcium, glucose, total protein, albumin, total bilirubin, AST, ALT, alkaline phosphatase) gamma-glutamyl transferase (GGT), prothrombin time (PT), activated partial thromboplastin time (aPTT), creatine kinase, amylase, cardiac troponin I. Urinalysis.
- Serum ferritin, serum iron, % transferrin saturation, TIBC: fasting blood collection
- Horomone Testing: LH, FSH, estrogen in WOCBP
- GLDH
- **Fecal Occult Blood:** Fecal sample is to be collected at home within 1 week prior to scheduled visit.
- C-SSRS

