# 6.8. Follow up: For Cohort 1, Visit 19 (Day 449±3) and for Cohort 2 and 3, Visit 11 (Day 225±3)

This visit will occur over 2 days.

- Physical Examination, including Nose and Throat Mucosal Exam.
- **Pregnancy Test**: A highly sensitive urine pregnancy test will be performed on all female subjects
- **Diary Cards:** For collection of first day of each menstrual cycle for WOCBP.
- Contraception Review: Confirmation of use of acceptable forms of contraception
- Weight
- Vital Signs: Supine blood pressure, pulse rate, respiratory rate, and oral temperature.
- 12-lead ECG: ECGs will be performed in triplicate
- Echocardiogram
- Clinical laboratory testing:

- Hematology with complete blood count and differential, comprehensive metabolic panel (sodium, potassium, chloride, carbon dioxide, blood urea nitrogen, creatinine, calcium, glucose, total protein, albumin, total bilirubin, AST, ALT, alkaline phosphatase) gamma-glutamyl transferase (GGT), prothrombin time (PT), activated partial thromboplastin time (aPTT), creatine kinase, amylase, cardiac troponin I. Urinalysis.
- Serum ferritin, serum iron, % transferrin saturation, TIBC: fasting blood collection
- Horomone Testing: LH, FSH, estrogen in WOCBP
- GLDH
- Fecal Occult Blood: Fecal sample is to be collected at home within 1 week prior to scheduled visit.
- C-SSRS
- **MRI-liver**: Liver MRI will be obtained for iron accumulation
- **MRI-muscle:** WB-MRI and dedicated thigh MRI will be performed for muscle quantity and quality
- **DXA Whole Body:** Whole body DXA will be performed for lean body mass assessment.
- **DXA Spine and Hip:** Spine and hip DXA will be performed for BMD.
- **Functional assessments:** Must be conducted in the following order: Respiratory function (FVC, FEV1, MIP, MEP), 4SC, 2MWT, 10-meter walk/run, TUG, strength assessment (MMT, hand-held dynamometry) and PUL.
- **Needle muscle biopsy:** Following WB-MRI and functional assessments, a needle muscle biopsy of the tibialis muscle will be performed.
- Quality of Life assessments
  - InQol
  - SF-36
- Immunogenicity sample collection.
- PD sample collection
- PK sample collection

- Adverse Event monitoring
- Infusion site reaction monitoring
- Concomitant medication

6.9. Follow-up: For Cohort 1, Visit 20 (Day 561±3) and for Cohort 2 and 3 Visit 12 (Day 337±3)

- Physical Examination, including Nose and Throat Mucosal Exam.
- **Pregnancy Test**: A highly sensitive urine pregnancy test will be performed on all female subjects

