- Diary Cards: For collection of first day of each menstrual cycle for WOCBP.
- Contraception Review: Confirmation of use of acceptable forms of contraception
- Weight
- Height
- Vital signs: Supine blood pressure, pulse rate, respiratory rate, and oral temperature.
- **12-lead ECG:** ECGs will be performed in triplicate
- Echocardiogram
- Clinical laboratory testing:
  - Hematology with complete blood count and differential, comprehensive metabolic panel (sodium, potassium, chloride, carbon dioxide, blood urea nitrogen, creatinine, calcium, glucose, total protein, albumin, total bilirubin, AST, ALT, alkaline phosphatase) gamma-glutamyl transferase (GGT), prothrombin time (PT), activated partial thromboplastin time (aPTT), creatine kinase, amylase, cardiac troponin I. Urinalysis.
- Serum ferritin, serum iron, % transferrin saturation, TIBC: fasting blood collection
- Horomone Testing: LH, FSH, estrogen in WOCBP
- GLDH
- **Fecal Occult Blood:** Fecal sample is to be collected at home within 1 week prior to scheduled visit.
- C-SSRS
- **MRI-liver**: Liver MRI will be obtained for iron accumulation
- **DXA Spine and Hip:** Spine and hip DXA will be performed for BMD.

- **Functional assessments:** Must be conducted in the following order: Respiratory function (FVC, FEV1, MIP, MEP), 4SC, 2MWT, 10-meter walk/run, TUG, strength assessment (MMT, hand-held dynamometry) and PUL.
- Quality of Life assessments
  - InQol
  - SF-36
- **Dosing**: study treatment administration
- Immunogenicity sample collection.
- PK sample collection
- PD sample collection
- **Biomarker collection:** Blood will be collected for proteomic, metabolomic, and genomic biomarker analysis
- Infusion site reaction monitoring.
- AE monitoring.
- Concomitant medication monitoring.
- 6.13. Telephone Follow-up: 30 +/-3days after final dosing visit
  - AE monitoring.
  - Concomitant medication

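### In the extension, about 82 of the 112 days of active SAE reporting have no planned contact, and the main-study follow-up length is stated in two incompatible ways

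*Protocol*

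**What the plan says.** **SAE window.** Protocol Section 8.2 starts active SAE reporting at consent and runs it "through and including 112 calendar days after the last administration of the investigational product". It adds two backstops. SAEs after the window are to be reported if the investigator learns of them. All AEs, serious or not, go on the CRF from the first dose through the subject's last visit.

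**Extension.** Dosing is 40 mg/kg every 4 weeks in all cohorts. After the last dosing visit (Visit 27, 22 or 18 for Cohorts 1, 2 and 3), Section 6.13 and Tables 3.1 to 3.3 schedule one contact, a call at "30 +/-3days after final dosing visit", covering AEs and concomitant medication.

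**Main study.** Section 3.2 describes follow-up as "ending 16 weeks after the last study dose in the treatment period". Section 3.1 counts from a different point: "At the conclusion of the treatment period, subjects will be followed for an additional 16 weeks". Section 6.4 and dosing Tables 3 and 4 put the last main-study dose on Day 197 (Cohorts 2 and 3) or Day 421 (Cohort 1). Section 6.9 puts the final follow-up visit on Day 337 or Day 561, with AE monitoring. The primary safety endpoints in Section 2.2.1 run to those same days.

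**The concern.** A reporting window finds events only if someone asks the subject about them. If the window extends well past the last planned contact, its later part depends on subjects volunteering information. In the extension that later part is most of the window.

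The stakes come from the protocol's own safety account. The extension uses the highest dose, with predicted margins to the monkey no-adverse-effect exposure of 2.2 for peak and 3.4 for average concentration (Section 1.10, Table 1). The liver is the organ of main concern, and in the monkey study at 284 mg/kg/week adverse liver findings were still present after a 13-week recovery (Section 1.7). Cohort 2 receives 40 mg/kg only in the extension, so the call is all the planned follow-up those 8 subjects have after that dose.

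In the main study the order is reversed: the window closes before the last visit. Two sections give follow-up lengths that cannot both be right for the same schedule, so a site cannot tell from the protocol when its active reporting duty ends relative to the final visit.

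**Working it through.** **Inputs**
- SAE window: 112 days after the last administration (Section 8.2).
- Last main-study dose: Day 197 (Cohorts 2 and 3), Day 421 (Cohort 1) (Section 6.4).
- Final main-study visit: Day 337, Day 561 (Section 6.9).
- Call after the last extension dose: day 30, window 27 to 33 (Section 6.13).
- Terminal half-life: about 12 to 19 days, in healthy adults (Section 1.8).

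**The plan's own figure.** 16 weeks × 7 = 112 days. The SAE window therefore equals the follow-up length worded in Section 3.2. The protocol does not say how 112 was chosen.

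**Extension: window end minus last planned contact**
- Nominal: 112 − 30 = 82 days; 82/112 = 73% of the window.
- Late call (day 33): 112 − 33 = 79 days. Early call (day 27): 112 − 27 = 85 days.
- All times are counted from the last dose, so the result is the same in all three cohorts.
- CRF recording ends at the last subject visit. That is the last dosing visit or, if the call is treated as a visit, about day 30. It does not cover days 31 to 112 on either reading.

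**Main study: last dose to final visit**
- Cohorts 2 and 3: 337 − 197 = 140 days. Cohort 1: 561 − 421 = 140 days. 140/7 = 20 weeks, against 16 in Section 3.2.
- The first post-dosing visit is Day 225 or 449, which is 28 days after the last dose and the end of a 32-week treatment period. From there, 337 − 225 = 112 and 561 − 449 = 112 days, so the schedule agrees with Section 3.1.
- Window end: 197 + 112 = Day 309; 421 + 112 = Day 533.
- Gap to final visit: 337 − 309 = 28 days; 561 − 533 = 28 days; 28/140 = 20% of the interval. If both visits move by up to 3 days, the gap is 22 to 34 days.

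**Who has the 28-day gap.** Subjects who receive all main-study doses and do not enter the extension. For those who enter, the last administration becomes the last extension dose and the 82-day figure applies. Entry is optional and follows the follow-up period, so on Day 310 a site may not yet know which case it has.

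**Drug remaining, as context.** Assuming simple exponential decline at the stated half-lives:
- Day 30: 2^(−30/12) = 0.18 and 2^(−30/19) = 0.33, so 18% to 33% remains.
- Day 112: 2^(−112/12) = 0.0015 and 2^(−112/19) = 0.017, so 0.15% to 1.7% remains.

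**The case against.** **The main-study gap loses little, if anything.** This stands. Section 8.2 keeps SAEs on the CRF through the final visit, Section 6.9 schedules AE monitoring there, and known later SAEs are still to be reported. A reader might infer that primary endpoint events are lost between Day 309 and 337, or Day 533 and 561. The documents do not support that: CRF recording covers those days. By day 112 little drug is left in any case.

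**The 112 days does match a stated follow-up.** This also stands. It equals the Section 3.2 wording. It would be wrong to say that it matches no follow-up in the protocol; it conflicts with the visit schedule. Nor do the documents show that the window was copied from the wrong figure.

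**Extension subjects are not out of contact.** This stands in part. There are 7, 10 or 6 extension dosing visits with AE monitoring, Section 6.14 allows unscheduled visits, Section 8.1 provides for following known AEs to resolution, and Section 8.14.1 covers SAEs learned of late. So the call is not the only extension contact, and it is too strong to say that nobody contacts the subject. But after the last dose these provisions act only on an event someone has already raised. None schedules a question to the subject after the call.

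**40 mg/kg is already followed for 140 days in Cohorts 1 and 3, and the primary endpoints stop before the extension.** Both are true, and they limit the consequence. They do not cover Cohort 2 after 40 mg/kg, or the longer cumulative exposure in Cohorts 1 and 3.

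**The half-life figures are rough.** They are: the profile is bi-phasic and comes from healthy adults, and with 28-day dosing, day 30 is close to an ordinary trough. The 82-day gap does not depend on them.

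**Conclusion.** The point holds, with most of its weight on the extension. There, about 82 of 112 days (73%; 79 to 85 days with the call window) of the active SAE window have no planned contact, and neither backstop in Section 8.2 fills the gap. This weakens ascertainment of late SAEs after the highest dose. It does not affect the primary endpoints, and it does not mean that SAEs cannot be reported.

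In the main study there is a 28-day mismatch (22 to 34 days with visit windows) between the end of active reporting and the final visit. It applies to subjects who complete dosing and do not enter the extension. It is a conflict of wording and reporting rules, and no data loss follows from it.

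A reader might also conclude that Section 3.2 is simply wrong and 20 weeks is right. The schedule and Section 3.1 agree with each other, but the documents do not settle which interval is meant to govern safety follow-up, so that stays with the sponsor.

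The figures rest on nominal visit days and on the tables listing every planned contact.

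**What to change.** Reconcile Protocol Sections 3.1, 3.2, 6.9, 6.13 and 8.2 (and Tables 3.1 to 3.3) so that three things are stated once and agree:
- the event from which main-study follow-up is counted, and its length;
- the end of active SAE reporting and the last planned contact, made to coincide in the main study and, separately, in the extension;
- whether the follow-up call counts as the last subject visit for CRF recording of AEs.

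Which interval governs is for the sponsor to decide.

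The cost is protocol wording and at most one re-timed or additional telephone call per extension subject. No main-study visit, endpoint or analysis needs to change.

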## 2.2. Endpoints

## 2.2.1. Primary Safety

- Incidence of dose limiting or intolerability treatment related AEs by day 337 or 561.
- Incidence, severity and causal relationship of treatment emergent AEs (TEAEs) and withdrawals due to TEAEs by day 337 or 561.
- Incidence and magnitude of abnormal laboratory findings (clinical laboratory tests [hematology, chemistry], GGT, GLDH, PT, aPTT, creatine kinase, amylase, serum ferritin, serum iron, % transferrin saturation, Total Iron Binding Capacity (TIBC), LH, FSH, estrogen, cardiac troponin I, fecal occult blood and urinalysis) by day 337 or 561.
- Abnormal and clinically relevant changes in liver MRI and physical examinations, weight, vital signs, ECG, echocardiogram measured LVEF, DXA (bone mineral density), menstruation cycle (as monitored by diary), and C-SSRS (See Appendix 1 and Appendix 2) parameters by day 337 or 561.

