## 6.2. Lead-in Period: Visit 2 (Baseline Day -111 to -110 prior to dosing on Day 1)

The following procedures and studies should be performed in the morning (before noon) of Visit 2 whenever possible

- Physical Examination, including Nose and Throat Mucosal Exam
- **Pregnancy Test**: A highly sensitive urine pregnancy test will be performed on all female subjects and must be confirmed as negative within 1 month of receiving first dose.
- Diary Cards: For collection of first day of each menstrual cycle for WOCBP.
- Contraception Review: Confirmation of use of acceptable forms of contraception
- Height: Height should be measured in the morning.
- Weight
- Vital signs: Supine blood pressure, pulse rate, respiratory rate, and oral temperature.
- Horomone Testing: LH, FSH, estrogen in WOCBP
- GLDH
- C-SSRS
- **MRI-muscle:** WB-MRI and dedicated thigh MRI will be performed for muscle quantity and quality

The following procedures should be performed in the afternoon of Visit 2 whenever possible:

- **DXA:** Whole body DXA will be performed for lean body mass.
- **Functional assessments:** Must be conducted in the following order: Respiratory function (FVC, FEV1, MIP, MEP), 4SC, 2MWT, 10-meter walk/run, TUG, strength assessment (MMT, hand-held dynamometry) and PUL.
- **Needle muscle biopsy:** Following WB-MRI and functional assessments a needle muscle biopsy of the tibialis muscle will be performed.
- PD sample collection

- **Biomarker collection:** Blood will be collected for proteomic, metabolomic, and genomic biomarker analysis
- Adverse event monitoring
- Concommitant medications

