6.1.3. Adverse Events

Severity is the key baseline information for adverse events. To judge an increase in adverse event severity after dosing, the post-dosing adverse event severity will be compared to the adverse event severity reported prior to the first day of study drug administration will be used.

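### Adverse events go on the CRF only after the first dose, so the SAP's comparison with pre-dose severity has no reference for nonserious lead-in events

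*Protocol*

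**What the plan says.** Protocol 8.2 sets two start dates. For sponsor safety reporting, "For SAEs, the active reporting period to Pfizer begins from the time that the subject provides informed consent". For the database, serious and nonserious AEs are entered on the CRF "from the time the subject has taken at least 1 dose of study treatment through the last subject visit".

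SAP 6.1.3 states that "Severity is the key baseline information for adverse events" and that "the post-dosing adverse event severity will be compared to the adverse event severity reported prior to the first day of study drug administration". Neither document defines the term treatment-emergent. SAP 6.1 adds one attribution rule: each AE is assigned to the treatment last received before its onset.

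The first of the four primary safety bullets in Protocol 2.2.1 concerns dose-limiting or intolerable treatment-related AEs. The second is "Incidence, severity and causal relationship of treatment emergent AEs (TEAEs) and withdrawals due to TEAEs by day 337 or 561". SAP 4.2.1 repeats both.

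Protocol 6.2 lists "Adverse event monitoring" among the Visit 2 procedures at Day -111 to -110, and the Schedule of Activities marks the same cell in the lead-in column. At Visit 3, Protocol 6.3 lists AE monitoring only among the procedures that follow dosing.

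**The concern.** The SAP names a baseline that the protocol's recording rule does not collect. If 8.2 is followed, the AE pages hold nothing from the lead-in, and severity is graded on those pages (Protocol 8.8).

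The disease makes this more than a formality. Protocol 8.3 counts worsening of the underlying disease as an AE, and the population has a progressive muscle disorder, so complaints that exist before Day 1 and fluctuate afterwards are to be expected. Without a graded pre-dose record, two errors are possible. A long-standing complaint first written down after dosing can be counted as new. A complaint that truly worsened on drug can be set aside as pre-existing. With cohorts of 4, 8 and 8 and no concurrent control, a single such subject is visible in the incidence table. Appendix 1 of the SAP plans eight TEAE tables (14.1.1.13 to 14.1.1.20).

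**Working it through.** There is no stated figure to reproduce. The check sets the passages side by side and then sizes the gap.

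**Is the pre-dose severity collected anywhere else?**

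1. *AE pages of the CRF.* Protocol 8.2 opens them after the first dose. Sections 8.1 and 8.14.2 speak of all AEs without a dosing limit, and 6.2 schedules AE monitoring at Visit 2. The protocol therefore disagrees with itself, and 8.2 is the only passage that gives a CRF start date.
2. *SAE reporting from consent.* This covers serious events only. Section 8.6.1 also takes loss of mobility or ambulation, muscle weakness, cardiomyopathy and fracture out of routine SAE reporting, unless judged drug-related, and relies on the CRF to capture them as AEs. In the lead-in there is no drug to relate them to and, under 8.2, no CRF recording, so these expected events fall outside both routes.
3. *Medical history.* It is taken at Screening only (6.1), covers significant histories and illnesses needing specialist care or treatment, and has no stated severity grade.
4. *Physical examinations and medication records.* These help to show that a condition existed before dosing. No severity grade is stated for them.
5. *Visit 2 monitoring, if it did reach the CRF.* It is one contact at the start of the lead-in. No pre-dose AE check is listed at Visit 3, so severity just before Day 1 would still be missing.

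**What can still be classified?**

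| Event | Classifiable from the CRF as written? |
|---|---|
| Clear onset after the first dose | Yes, by onset date (SAP 6.1) |
| Nonserious, present before dosing, possibly worse afterwards | No, there is no graded pre-dose record |
| First recorded after dosing, onset uncertain | No, new and pre-existing cannot be told apart |

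**Size of the unrecorded window.** Inputs are 20 planned subjects (4 + 8 + 8) and a lead-in of about 16 weeks (Protocol 3.1).

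- 20 x 16 = 320 subject-weeks, and 320 / 52.2 = about 6.1 subject-years.
- The figure rises if the Cohort 2 lead-in is extended, which the Schedule of Activities footnotes allow.

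**Effect of one misclassified subject on overall TEAE incidence**, provided that the subject has no other TEAE:

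- Cohort 1: 1/4 = 25 percentage points.
- Cohorts 2 and 3: 1/8 = 12.5 percentage points each.

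**The case against.** The strongest reply is that a reader might infer from this conflict that treatment-emergence, and with it the primary endpoint, cannot be determined. The documents do not support that. Events that start after the first dose are classified by date under SAP 6.1. TEAEs are also only part of the primary safety endpoint: laboratory, ECG and echocardiogram data have their own pre-dose baselines (SAP 6.1.1 and 6.1.2), and liver MRI is done at Screening. This stands, and it limits the point to the events in the last two rows of the table.

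A reader might also want a number of false TEAE cases. None can be derived. The documents give no rate of complaints ongoing at Day 1, and not every such subject would be misclassified. The 320 subject-weeks measure the recording gap, not bias. The 25 and 12.5 point shifts apply only to a subject with no other TEAE.

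The pre-dose muscle biopsies are a minor source. Protocol 1.12.7 puts their combined risk below 1%, so two per subject before dosing (2 x 20 = 40) imply fewer than 0.4 expected events. Complications of the Visit 3 biopsy that appear after dosing fall inside the CRF window.

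Nor is the lead-in the only drug-free AE observation. Follow-up runs from the last dose at Day 197 to Day 337 in Cohorts 2 and 3. That is 140 days, or 140/19 = 7.4 to 140/12 = 11.7 of the half-lives in Protocol 1.8. It supplies off-drug data but no pre-treatment severity.

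Finally, SAP 8.2 defers AE summaries to sponsor data standards. Neither these nor the CRF are in the documents, and they may contain a TEAE rule. A derivation rule cannot supply a severity that was never recorded, however, so the conflict between 8.2 and SAP 6.1.3 remains.

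**Conclusion.** The conflict is real and should be fixed. Protocol 8.2 contradicts the AE monitoring scheduled at Visit 2 and leaves SAP 6.1.3 without its reference for nonserious events present before dosing. The consequence is confined to judging worsening of those events and to telling new from pre-existing conditions first recorded after dosing. Misclassification can inflate or deflate TEAE incidence, and the documents do not show which is likelier or how often it would occur. The conclusion assumes that 8.2 is followed literally. If sites enter Visit 2 events regardless, the gap narrows but does not close, because no pre-dose AE check is listed at Visit 3.

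**What to change.** - **Protocol 8.2:** start CRF recording of serious and nonserious AEs, with onset date and severity, at informed consent, or at the latest at Visit 2.
- **Protocol 6.3:** add an AE check before dosing at Visit 3, so that severity immediately before Day 1 is on record.
- **SAP 6.1.3:** define a TEAE as an event with onset on or after the first dose, or one that worsens from its recorded pre-dose severity.
- **If lead-in AEs cannot be recovered:** define TEAEs by onset only, remove the severity comparison from SAP 6.1.3, and state in the report that worsening of pre-existing events could not be assessed.

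The cost is a few sentences in each document and a little more AE data entry during the lead-in. Visit 2 monitoring is already scheduled, and Visit 3 already takes place before dosing, so no extra visit is needed.
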